7 STATISTICAL METHODOLOGY FOR SAFETY

Patients are evaluable for general safety if they received any study treatment. Safety will be evaluated in each arm separately according to the actual treatment received.

7.1 Toxicity and adverse events

All the adverse events will be coded using the Medical Dictionary for Regulatory Activities (MedDRA).

The toxicity evaluation will be coded with the National Cancer Institute-Common Toxicity Criteria (NCI-CTC), version 4.

As far as all the toxicities are concerned, the NCI-CTC grade will be used wherever an NCI-CTC grading exists. Otherwise, the severity will be noted. As a convention, the term «Grade» will always be used. Toxicities will be described according to the worst NCI-CTC grade or, for toxicities which do not form the subject of NCI-CTC classification, according to the worst severity.

Summary of overall adverse events will be done by body system and preferred term, by severity (worst toxicity grade), by relationship to the study drug/s, and by AE outcome. Tables will be sorted by body system/preferred term and by the highest incidence.

A frequency table will be made for the AEs leading to cycle delay, dose reduction, skipped dose, or withdrawal of study medication. Adverse events with outcome of death will also be presented by relationship to the study drugs.

7.2 Clinical laboratory evaluation

Laboratory results will be classified according to the NCI-CTC version 4.

For hematology values: absolute neutrophil count, lymphocyte count, WBC count, platelet count and hemoglobin worst grade per patient and per cycle will be displayed.

Overall cross tabulation will be presented for the worst grade during treatment versus the baseline toxicity grading of anemia, lymphopenia, leukopenia, neutropenia and thrombocytopenia.

The worst grade per patient during treatment and per cycle will be also calculated for the biochemical tests: ALT, AST, Total bilirubin, AP, CPK, creatinine, calcium, potassium, sodium, glucose and albumin.

Time and duration of AST and ALT increases in cycles with grade 3-4 abnormality will be tabulated.

Overall cross tabulation will be presented for the worst grade during treatment versus the baseline toxicity grading of AST and ALT increase.

If appropriate, the laboratory abnormalities before and after crossover in patients who switch arm after progression will be compared descriptively.

7.3 Vital signs, physical examination, left ventricular ejection fraction (LVEF) and electrocardiogram findings

Tabulation will be made summarizing the performance status, body weight, LVEF and electrocardiogram abnormalities at baseline and during the treatment for each patient.

7.4 Deaths and other Serious Adverse Events

Deaths and other Serious Adverse Events will be tabulated.

8 OTHER ANALYSES

Non-continuous variables will be described in frequency tables using counts and percentages. Continuous variables will be described by median, minimum and maximum.

8.1 Baseline and demographic data

Baseline data such as demographics, multiple myeloma history, prior therapy, prior relevant history, signs and symptoms, electrocardiogram, LVEF, protein measurements, laboratory values and concomitant medication (ATC-WHO coded) will be described following standard tables detailed in Appendix I. When two or more assessments have been done for the same parameter, the last assessment before the first drug administration will be taken into account for the analysis.

8.2 Treatment administration

Total cumulative dose, time on treatment, dose intensity and relative dose intensity, cycle delay, and dose reductions will be described following standard tables detailed in Appendix I.

Total cumulative dose by drug, expressed in mg/m² for plitidepsin, or in mg of dexamethasone, is the sum of all the product doses from the first cycle until last cycle including the dose received in last cycle.

Patients will be considered to be on-treatment for the duration of their treatment and 30 days following the last treatment dose. Those patients in the control arm (Arm B) who crossed over to the combination arm (Arm A) after disease progression will be considered on-treatment for the duration of their whole treatment (dexamethasone alone + dexamethasone in combination with plitidepsin) and during the first 30 days following the last treatment dose. If the patient starts any new antitumor therapy outside this clinical trial or dies within 30 days of last treatment dose, the date of administration of this new therapy or the date of death will be considered the date of treatment discontinuation.

However, as a convention, for dose intensity calculation purposes, the duration of the last cycle is considered to be 28 days. If the patient starts any new antitumor therapy outside this clinical trial or dies within 28 days of last cycle initiation this will be taken into account for the calculation of the duration of the last cycle.

Intended dose intensity is the planned dose per cycle divided by the planned number of weeks by cycle (2.5mg/m²/wk for plitidepsin, 40mg/wk for dexamethasone).

Absolute dose intensity is the actual cumulative dose divided by the number of weeks of treatment. Relative dose intensity (%) is the ratio of absolute dose intensity divided by the intended dose intensity.

The item «Infusion delayed/ omitted: yes/no» in the case report form (CRF) will be used to calculate the delay (on day 1 infusion) or skipped infusions (on day 15 infusion). For cycles considered as delayed by the investigator, the delay will be calculated as:

Delay: Date of current drug administration – Date of previous drug administration – 28.

The first infusion of the first cycle will be excluded from all cycle delay and cycle modification calculations.

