7.2 ADMINISTRATION OF STUDY MEDICATION

The administration of each study medication will be as follows:

- Arm A:
 - a) Dexamethasone: 40 mg orally on Day 1, 8, 15 and 22 every four weeks (q4wk) at least one hour before plitidepsin infusion.
 - b) Plitidepsin: 5 mg/m² intravenously (i.v.) diluted to a total volume of 250 ml in 0.9% saline (or 5% glucose) via a central venous catheter (suggested) or diluted to a total volume of 500 ml in 0.9% saline (or 5% glucose) via a peripheral line. Infusion will be performed through a pump device over three hours (fixed rate) on Day 1 and 15 q4wk.
- Arm B:
 - a) Dexamethasone: 40 mg orally on Day 1, 8, 15 and 22 q4wk.

A cycle is defined as a four-week period.

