2 STUDY DESIGN

This will be a prospective, multicenter, open-label, two-arm, 2:1 randomized phase III study of plitidepsin in combination with dexamethasone vs. dexamethasone alone in patients with relapsed/refractory MM.

The primary study endpoint is progression free survival (PFS).

- Treatment Arm A:
 - Dexamethasone: 40 mg orally on Day 1, 8, 15 and 22 every four weeks (q4wk) at least one hour before plitidepsin infusion.
 - Plitidepsin: 5 mg/m² intravenously (i.v.) diluted to a total volume of 250 ml in 0.9% saline via a central venous catheter (suggested) or diluted to a total volume of 500 ml in 0.9% saline via a peripheral line. Infusion will be performed through a pump device over three hours (fixed rate) on Day 1 and 15 q4wk.

- Treatment Arm B:
 - Dexamethasone: 40 mg orally on Day 1, 8, 15 and 22 q4wk.

Patients in the control arm (dexamethasone alone, Arm B) who have documented disease progression after a minimum of eight weeks from randomization should be offered to cross over to combination arm (plitidepsin + dexamethasone, Arm A) upon Sponsor agreement.

Patients may be treated with additional cycles of plitidepsin and dexamethasone or dexamethasone alone, as long as no unacceptable toxicity and/or disease progression is documented.

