12.1 Extent of exposure

12.1.1 Treatment administration

Table 12.1.1.1 Number of cycles administered and dose intensity

No. of cycles administered per patient	Arm A		Arm B	
	N	%	N	%
1				
2				
3				
...				
Median (range)				
Time on treatment (weeks)				
Median				
Range				
Plitidepsin cumulative dose (mg/m ²)			NA	
Median				
Range				
Plitidepsin dose intensity (mg/m ² /wk)			NA	
Median				
Range				
Plitidepsin relative dose intensity (%)			NA	
Median				
Range				
Dexamethasone cumulative dose (mg)				
Median				
Range				
Dexamethasone dose intensity (mg/wk)				
Median				
Range				
Dexamethasone relative dose intensity (%)				
Median				
Range				

NA: Not applicable. Cycles after crossover will be excluded.

Table 12.1.1.2 Number of cycles administered and dose intensity after crossover

No. of cycles administered per patient	After crossover	
	N	%
1		
2		
3		
...		
Median (range)		
Time on treatment (weeks)		
Median		
Range		
Plitidepsin cumulative dose (mg/m ²)		
Median		
Range		
Plitidepsin dose intensity (mg/m ² /wk)		
Median		
Range		
Plitidepsin relative dose intensity (%)		
Median		
Range		
Dexamethasone cumulative dose (mg)		
Median		
Range		
Dexamethasone dose intensity (mg/wk)		
Median		
Range		
Dexamethasone relative dose intensity (%)		
Median		
Range		

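### SAP 8.2 shortens the last cycle at death or outside therapy but keeps every dose given, so patients dosed to plan can show relative dose intensity above 100%

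*SAP*

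**What the plan says.** SAP 8.2 defines the three components of RDI.

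- Numerator: cumulative dose per drug "is the sum of all the product doses from the first cycle until last cycle including the dose received in last cycle". Nothing is prorated for an incomplete last cycle.
- Absolute intensity: "Absolute dose intensity is the actual cumulative dose divided by the number of weeks of treatment".
- RDI: absolute intensity as a percentage of intended intensity, which is fixed at 2.5 mg/m²/wk for plitidepsin and 40 mg/wk for dexamethasone. No upper limit is stated.

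For this purpose the last cycle counts as 28 days. The exception covers a patient who begins outside antitumor therapy "or dies within 28 days of last cycle initiation this will be taken into account for the calculation" of its duration. The natural reading is that the cycle then ends on the date of that event. The SAP does not say whether the event day itself is counted.

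Table 12.1.1.1 has a row for "Plitidepsin relative dose intensity" and one for dexamethasone, each reported as median and range. Table 12.1.1.2 repeats the layout for treatment after crossover.

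**The concern.** Each dose is given at the start of the interval it is meant to cover: 14 days for plitidepsin and 7 days for dexamethasone. Cutting the denominator partway through an interval removes time that the dose was planned to cover, while the whole dose stays in the numerator. RDI then rises above 100% without any excess dose.

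The patients concerned are those who die or move to other therapy soon after starting a cycle. An exposure table that shows them as overdosed misdescribes delivery, and the inflation can partly hide an infusion that was due and not given. SAP 11.2 marks treatment compliance as not applicable, so RDI in these two tables is the plan's overall summary of dose delivered against dose intended.

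**Working it through.** **Inputs.** "Plitidepsin: 5 mg/m² intravenously (i.v.) diluted to a total volume of 250 ml", given "over three hours (fixed rate) on Day 1 and 15 q4wk" (SAP 2); "Dexamethasone: 40 mg orally on Day 1, 8, 15 and 22 q4wk" (SAP 2); "A cycle is defined as a four-week period" (Protocol 7.2); the definitions in SAP 8.2.

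**The plan's own figure.** Plitidepsin: 5 × 2 / 4 = 2.5 mg/m²/wk. Dexamethasone: 40 × 4 / 4 = 40 mg/wk. Both reproduce exactly.

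**Formula.** With k full 28-day cycles before the last one and t days counted in the cut cycle:

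RDI = [cumulative dose / (4k + t/7)] / intended intensity.

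Assumptions: every scheduled dose given on time, no delays, no dose on the day of the cut. Under these, delivery matches the plan.

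**Examples for plitidepsin.**
- Sole cycle, t = 8: 5 / (8/7) / 2.5 = 175%.
- Sole cycle, t = 17: 10 / (17/7) / 2.5 = 165%.
- One full prior cycle, t = 5: 15 / (33/7) / 2.5 = 127%.
- One full prior cycle, t = 1 (the largest value): 15 / (29/7) / 2.5 = 145%.
- Three full prior cycles, t = 1 (the largest value): 35 / (85/7) / 2.5 = 115%.

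**RDI (%) by day of cut, plitidepsin / dexamethasone.**

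| t (days) | k = 0 | k = 1 | k = 3 |
|---|---|---|---|
| 4 | 350 / 175 | 131 / 109 | 111 / 103 |
| 7 | 200 / 100 | 120 / 100 | 108 / 100 |
| 10 | 140 / 140 | 111 / 111 | 104 / 104 |
| 14 | 100 / 100 | 100 / 100 | 100 / 100 |
| 17 | 165 / 124 | 124 / 109 | 111 / 104 |
| 21 | 133 / 100 | 114 / 100 | 107 / 100 |
| 27 | 104 / 104 | 102 / 102 | 101 / 101 |

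The excess is zero when the cut falls on a dosing boundary: day 14 for plitidepsin; days 7, 14 and 21 for dexamethasone. The dexamethasone maximum over cut days 1 to 27 is 121% for k = 1 and 107% for k = 3.

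**Day count.** If the event day is also counted, the sole-cycle plitidepsin values at 4, 7, 10 and 14 days become 280%, 175%, 127% and 93%. The unstated convention therefore changes the result.

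**Masked omission.** Cycle 1 without its Day 15 infusion, Day 1 of Cycle 2 given, t = 8: 10 / (36/7) / 2.5 = 78%. Infusions given over infusions due: 2/3 = 67%.

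**A rule that respects dosing intervals.** End the denominator 14 days after the last scheduled plitidepsin day, or 7 days after the last scheduled dexamethasone day, on or before the cut.
- Sole cycle, t = 8, plitidepsin: 5 / 2 / 2.5 = 100%.
- Sole cycle, t = 17, plitidepsin: 10 / 4 / 2.5 = 100%.
- Sole cycle, t = 10, dexamethasone: 80 / 2 / 40 = 100%.
- Masked omission: 10 / 6 / 2.5 = 67%.

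**The case against.** The other side has several fair points.

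- **Few patients may be affected.** Only death or therapy outside the trial within 28 days of starting the last cycle triggers the cut. Crossover does not. Myeloma protein is assessed on Day 1 of each cycle, so a patient stopped for progression at that visit, before dosing, has already completed 28 days. This stands. The number affected cannot be derived from the documents.
- **The effect fades.** After three full cycles the excess is at most about 15% for plitidepsin and 7% for dexamethasone. This stands. Delays, omissions or reductions can also offset it.
- **Other tables show delivery.** Cumulative dose, delays, omissions and reductions are reported separately in SAP 12.1.1 to 12.1.4. This limits the harm but does not make the RDI value right.
- **RDI is a convention.** Dose per week of treatment is a legitimate measure. But the SAP divides it by an intended intensity averaged over a full cycle, and that ratio is interpretable only if the denominator covers whole dosing intervals.
- **Dividing by the dose planned up to the end of treatment, for everyone, would do harm.** If the end is the stop date, a patient stopped for toxicity after one infusion would move from 50% to 100%. This stands, and is why the change should be confined to cut cycles.

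A reader might also infer that the reported range is meaningless, or that dexamethasone RDI cannot be compared between arms. The documents support neither. The inflation mainly exposes the maximum. The arms could differ in how often patients leave early for outside therapy, but no frequencies are given. Nor can a typical bias be taken from the planning assumptions. The control medians of 10 to 16 weeks are PFS scenarios, and plitidepsin RDI does not apply in Arm B. The matching Arm A scenarios of 16 to 25.6 weeks correspond to roughly 4 to 6 cycles, where the excess is small.

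**Conclusion.** The rule as written gives wrong values for a definable group: patients whose last cycle is cut by death or outside therapy between dosing boundaries. The distortion is large when the cut falls early in a sole cycle (plitidepsin 140% to 350% for cuts at 10 down to 4 days), moderate after one full cycle (up to about 145%) and small after three. Dexamethasone is affected less because it is dosed weekly. A true shortfall can also be understated, 78% against 67% in the example.

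It would be a mistake to read this as RDI being far above 100% in general. How far the median in Table 12.1.1.1 or 12.1.1.2 would move is unknown, because neither the number of such patients nor their distribution over cycles is given. The maximum is most exposed, since one early death can set it. RDI is descriptive and carries no test; PFS, OS, alpha and sample size are unaffected. The figures assume on-time dosing, no delays, no dose on the day of the cut, and that taking the event into account means ending the cycle on its date.

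**What to change.** Keep the 28-day convention for every patient whose last cycle is not cut by death or outside therapy, including those who stop for toxicity. Where it is cut, amend SAP 8.2 so that the denominator for each drug ends with the dosing interval of the last dose scheduled on or before the cut: 14 days after the last scheduled plitidepsin day and 7 days after the last scheduled dexamethasone day.

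State the day count, and whether a dose scheduled on the day of the cut counts as due. The second choice matters. With a sole cycle cut on Day 15 before infusion, plitidepsin RDI is 5 / 2 / 2.5 = 100% if that dose is not due and 5 / 4 / 2.5 = 50% if it is. Apply the same rule in Tables 12.1.1.1 and 12.1.1.2.

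Simply using 28 days for everyone is not a good substitute. A patient who died 7 days after the first infusion would score 5 / 4 / 2.5 = 50%, with a dose not yet due counted as missed.

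The cost is one SAP sentence, a small programming change and a denominator that can differ between the two drugs in the same patient. No new data are needed.

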8.3 Subsequent therapy

A table summarizing the subsequent therapies received after treatment discontinuation will be shown.

Time to first subsequent therapy or death will be analyzed as a measure of the time from randomization to treatment failure that leads to the need of a further treatment regimen (regardless the method of PD detection or the components of the PD).

8.4 Protocol deviations

Analysis of inclusion/exclusion criteria deviations, retreatment restrictions, used concomitant medication and clinically relevant discontinuations will be done as described in Appendix I.

8.5 Pharmacokinetic analyses

Methods for pharmacokinetics will be described in a separate document.

8.6 Imputation of incomplete dates

The dates of certain historical or current clinical activities are key component for statistical analysis. Incomplete date appears when day, month or year is/are missing, and it could be imputed so that variables like time to and duration of certain event can be calculated. If none of day, month and year is available, then the date is missing, no imputation is necessary.

Before randomization

If day of a date is unknown then the imputed day will be 15, if the month is also unknown then the imputed date will be July 1st. This assumption will be valid if the imputed date is earlier than the randomization date; otherwise the imputed date will be the first day of the randomization month if only the day is missing, or the 15th day of the month prior to the randomization date (i.e. 15/Month of randomization date - 1/Year) if day and month are missing.

After end of treatment

To ensure the most conservative approach for the main time-to-event variables (i.e. PFS and OS) that can be affected by missing values the following rules will be implemented: if the day of a date is unknown then the imputed day will be 1. This assumption will be valid if the imputed date occurs later than the last drug administration date; otherwise the imputed date will be the last drug administration date plus 1 day.

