5.12 EVALUATION AT THE END OF TREATMENT

The end-of-treatment visit will be scheduled 30 days (\pm two days) after the administration of the last dose of the study therapy, unless another anticancer treatment is started before. In that case, the end-of-treatment visit should be performed immediately before the start of the new therapy (ideally the day before or the same day).

At the time of patient discontinuation (regardless of the reason), the same complete work-up done before study entry will be repeated.

- Physical examination, weight and height.
- ECOG performance status.
- Vital signs.
- Hematology and coagulation tests.
- Biochemistry (A and B).
- ECG: It should allow rhythm definition (at least 30 seconds of duration)
- LVEF assessment by ECHO or MUGA.
- Safety assessment (AEs).
- Serum protein: serum protein electrophoresis, immunoglobulins quantification, M-protein identification and quantification, and serum sFLC if indicated.
- Urine protein: Only if Bence-Jones proteinuria is present at entering the study.
- Serum β -2 microglobulin: only if the patient discontinues treatment without documented disease progression.
- Bone marrow (if clinically indicated).
- Radiological tumor assessment only in case of soft tissue plasmacytoma present at entering the study.
- Skeletal evaluation.
- Concomitant treatments.

Adverse events must be assessed for 30 days after the administration of the last study treatment. All SAEs occurring within 30 days of the last study drug administration will be reported. Beyond this period of time, only those suspected to be treatment-related SAEs will be reported (Section 9.2.2).

The Sponsor will evaluate any safety information that is spontaneously reported by an Investigator beyond the time frame specified in the protocol.

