An external review committee blinded to treatment arm will assign the objective response and a progression or censoring date for each patient based on laboratory data, radiologic and bone marrow assessments when required and evaluation of all relevant clinical information; then, this information will be merged with the date of death from the death report forms and with further antitumor therapy data for the calculation of PFS. Patients with missing IRC evaluations will have their PFS censored at randomization date.

The primary study analysis will be based on externally assessed PFS data in the “All Randomized Patients” population, defined as all patients randomized to either treatment arm.

By design, disease response will be assessed every four weeks symmetrically across treatment arms irrespectively of treatment delays or omissions. Disease assessments (e.g., serum or urine M-spike, sFLC) and evaluation of extent of disease will be done within two weeks before randomization and every four weeks thereafter in the absence of PD while on treatment. If disease progression has not occurred at treatment termination, then disease assessments should continue every four weeks until evidence of disease progression or other antitumor therapy, whichever occurs first, and then will be followed every three months for survival until death, or until the date of study termination, whichever occurs first.

Study termination date is defined as the date in which 80% of death events occurred, 24 months after the accrual of the last randomized patient, or IDMC recommendation (whichever occurs first).

PFS and objective tumor response will be assessed according to IMWG criteria. Centralized laboratory reports and copies of computed tomography scans (CT-scans), magnetic resonance imaging (MRI) (in case of soft tissue plasmacytoma) and any other documented means to evaluate tumor response or progression should be available for IRC review.

For patients within the “All Crossover Patients” dataset, the PFS is defined as the time from the day of the last disease assessment, before the first administration of the combination, to the date of documented progressive disease (PD) by IMWG criteria or death (regardless of the cause of death). The same censoring rules described above for PFS calculation will be considered.

Secondary endpoints.

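### The partial-date rule in SAP 8.6 checks an imputed death date only against the last dose, so a death with unknown day can be dated before a documented contact at which the patient was alive

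*SAP*

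**What the plan says.** SAP 8.6 gives separate rules for dates before randomization and after end of treatment. The second is introduced with the words "To ensure the most conservative approach for the main time-to-event variables (i.e. PFS and OS) that can be affected by missing values". Its content is "if the day of a date is unknown then the imputed day will be 1", followed by one check: "This assumption will be valid if the imputed date occurs later than the last drug administration date". If the check fails, "otherwise the imputed date will be the last drug administration date plus 1 day".

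No other place adds a lower bound. The PFS and OS definitions in SAP 6.1.2 contain no ordering rule, and SAP 8.8 deals only with tabulating missing values.

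Both documents schedule dated contacts after the last dose:
- Protocol 5.12: "The end-of-treatment visit will be scheduled 30 days" after the last dose, with a two-day tolerance.
- SAP 6.1.2: "If disease progression has not occurred at treatment termination, then disease assessments should continue every four weeks until evidence of disease progression", unless other antitumor therapy starts first.
- SAP 6.1.2: patients "then will be followed every three months for survival until death" or study termination.

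SAP 6.1.2 also states that death dates from the death report forms are merged with the IRC dates to calculate PFS. An imputed death date can therefore enter the primary endpoint as well as OS.

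**The concern.** The last dose is a valid lower bound for a death date, but it need not be the best one in the database. Any later visit, assessment or survival contact shows that the patient was still alive, and the rule uses none of them. Followed exactly, it can record a death on a day when another form shows the patient attending a visit.

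At stake is the internal consistency of OS and of PFS events that are deaths. Two planned analyses would inherit the error. The midpoint sensitivity analysis of PFS (SAP 6.1.2) averages the last progression-free assessment and the death date. The two-stage crossover adjustment (SAP 6.2.3) models survival after progression, which cannot be negative.

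The pre-randomization rule in the same section does check the imputed date against a relevant milestone, so the principle of an ordering check is already accepted.

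**Working it through.** The plan states no figure to reproduce. The check applies the rule to worked dates and then to simulated follow-up.

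**Rule as written.** Let L be the last dose date and D1 the first day of the recorded month. Imputed date = D1 if D1 > L; otherwise L + 1 day.

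**Worked dates (illustrative)**

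| Last dose | Later documented contact | Recorded event | Imputed date | Distance before the contact |
|---|---|---|---|---|
| 10 Mar 2014 | Alive at end-of-treatment visit, 9 Apr (10 Mar + 30 days) | Death, Apr 2014 | 1 Apr | 8 days |
| 3 Apr 2014 | Seen alive 20 Apr | Death, Apr 2014 | 4 Apr (fallback) | 16 days |
| 10 Mar 2014 | Progression-free 7 May | Progression, May 2014 | 1 May | 6 days |

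Both branches of the rule can fail.

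**Knock-on effects**
- Midpoint analysis: if the 9 April visit in the first row is also the last progression-free assessment, the event is placed midway between 9 April and 1 April. That is 9 April − 8/2 days = 5 April, before the assessment that showed no progression.
- Two-stage analysis: last dose 8 April, progression 15 April, death in April gives an imputed death on 9 April. Survival after progression is 9 − 15 = −6 days.

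**Simulated frequency.** Assumptions, none of them from trial data: death uniform over days 31 to 399 after the last dose; first contact at day 30; further contacts every 91 or every 28 days; day of death missing.

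| Contact interval | Share of day-missing deaths placed before the last contact | Mean error when out of order | Maximum |
|---|---|---|---|
| 91 days (three-monthly) | 16% | 10.4 days | 29 days |
| 28 days (four-weekly) | 50% | 10.2 days | 29 days |

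For a partial progression date found at the next four-weekly visit (± 2 days), the share is about 6%.

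**What a floor at last known alive changes.** An out-of-order death moves to the day after the last contact, so the average gain over all day-missing deaths is about share × (mean error + 1).
- Three-monthly: 0.161 × (10.4 + 1) ≈ 1.8 days. The mean distance between imputed and true death falls from 14.7 to about 12.9 days.
- Four-weekly: 0.495 × (10.2 + 1) ≈ 5.6 days, from 14.7 to about 9.1 days.

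Out-of-order dates fall to zero by construction. The first two worked cases become 10 April and 21 April.

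**The case against.** The strongest objection is that this is small and mostly confined to OS, which is secondary and not the powered endpoint. That stands. Four stronger readings that a reader might infer are not supported.

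- **That primary-endpoint progression dates are commonly affected.** The IRC assigns progression from laboratory, imaging and marrow assessments, with protein assays done centrally. Those dates are rarely partial, and with four-weekly visits a progression-free and a progressing assessment seldom share a month. For PFS, the practical route is a partial death date without earlier progression. That route is narrowed further because deaths after more than one missed follow-up are censored.
- **That the error is about 15 days per date.** That figure is the ordinary effect of any day-1 imputation. The ordering error is smaller and less frequent, and the proposed floor leaves much of the shift in place.
- **That most deaths fall long after the last dose, so the check is nearly useless.** The documents give no such figure; SAP Listing 12.3.2.2 has a column for time from last dose but is an empty shell. If it were true, with three-monthly contacts, last contact and death would seldom share a month and out-of-order dates would be the minority case.
- **That the rule favors one arm because early dates are not conservative for a comparison.** The rule is the same in both arms and no direction of bias is shown. The label is loose, but the replacement also defaults to day 1 and is open to the same remark.

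The four-week-grid and interval-censoring analyses of PFS also limit how far PFS conclusions could depend on a few days. They do not correct an out-of-order death, and they do not cover OS.

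**Conclusion.** The point holds for death dates with an unknown day. Applied as written, SAP 8.6 can place a death before a documented contact at which the patient was alive, and nothing else in the SAP prevents it. OS is affected, as is PFS where death is the event; for IRC-assessed progression the problem is marginal.

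Under assumed three-monthly contacts and uniform death times, about one in six day-missing deaths would be out of order, by roughly 10 days on average and at most 29. The 50% share applies only with four-weekly contacts. Off treatment, the Protocol (5.1, 5.13) schedules those for patients without progression or with unresolved toxicity. The number of partial dates is not given, so no effect on a hazard ratio can be calculated. This is a low-priority correction of a rule that gives wrong dates in identifiable cases, not a threat to the trial's conclusions.

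**What to change.** Replace the post-treatment rule in SAP 8.6 with one sentence: when only the day is missing, impute the latest of (a) day 1 of the recorded month, (b) the day after the last drug administration and (c) the day after the last date known alive, kept within the recorded month. For a partial progression date, (c) becomes the day after the last assessment without progression.

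The cost is one SAP sentence and a small programming change, using dates already collected. The rule can be applied to the extended survival follow-up described in Protocol 10.2.3.4, with any death dates already imputed listed and checked against last contact. Reporting the number of imputed dates by arm would settle whether the point has any practical effect.
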